**Study Title: Self-Administered Gerocognitive Examination (SAGE) for the Early Detection
of Cognitive Impairment at Primary Care Provider Visits**

NCT #: NCT04063371

February 18, 2020

PROTOCOL

Self-Administered Gerocognitive Examination (SAGE) for the Early Detection of Cognitive Impairment at Primary Care Provider Visits

February 18, 2020

Introduction

Memory deficits are common in the elderly and can be contributed to normal aging, neurodegenerative disorders, acute illnesses or other etiologies. Mild Cognitive Impairment (MCI) is a condition where individuals display cognitive impairments that are more than expected with normal aging, but not severe enough to interfere with daily function (Burke, Sengoz, & Schwatz, 2000; Portet et al., 2006). Symptoms of MCI may be reversible, some may remain stable and some may progress to neurodegenerative disorders such as Alzheimer's disease (Scharre & Trzepacz, 2013). Conditions such as depression, sleep apnea and vitamin B deficiency can affect one's memory and thinking and be reversible (Scharre & Trzepacz, 2013). Once identified, treatments can be initiated to improve the cognitive impairment that is associated with these disorders. Approximately 11% of MCI cases are reversible (Scott & Barrett, 2007). Reversal of the cognitive impairments can improve an individual's quality of life (van den Dungen et al., 2016). Approximately 10-15% of Mild Cognitive Impairment cases progress to Alzheimer's disease (Janoutova, Sery, Hosak, & Janout, 2015; Yue et al., 2012).

Cognitive impairment is becoming increasingly prevalent across the world. The increase in life expectancy is thought to contribute to this rise. An estimated 5.2 million individuals in the United States and 46.8 million individuals worldwide are currently living with dementia (Alzheimer's Disease International [ADI], 2016; Barnes et al., 2014). This number is expected to increase by 9.9 million each year, doubling after 20 years (ADI, 2016; Prince et al., 2013). By 2050 it is estimated that there will be 131.1 million individuals with dementia worldwide (ADI, 2016; Khanassov & Vedel, 2016). Alzheimer's disease is the most common type of dementia accounting for 60-80% of all dementia cases (Alzheimer's Association, 2015; Alzheimer's Association, 2017; Manenti et al., 2004). 50-75% of the current dementia cases are undiagnosed (Barnes et al., 2014; Eichler et al., 2015). Often, adults who experience subjective memory complaints do not discuss the symptoms with their physician (Adams, 2016). The average time of diagnosis is 32 months after the onset of symptoms (Jost & Grosberg, 1995; Van Vliet et al., 2013). Early diagnosis of cognitive impairment can be beneficial the following reasons: treatable causes can be reversed; pharmacological interventions can be initiated earlier; and the individuals can play an active role in the decision-making planning for their future (Adams, 2016). Alzheimer's therapeutics have also been shown to be more effective when initiated early (Yiannopoulou & Papageorgiou, 2013).

The 2010 Patient Protection and Affordable Care Act added an Annual Wellness Visit (AWV) as a Medicare benefit for Medicare recipients. As part of the Annual Wellness Visit medical providers review and update the patient's medical history, surgical history, current medications and list of current medical providers; they conduct routine measurements of height, weight, body-mass index (BMI) and blood pressure; they conduct an assessment to detect cognitive impairment; and they conduct a health risk assessment (Cordell et al., 2013; U.S. Government Publishing Office, 2016). Per the regulation, the cognitive impairment can be assessed through direct observation of the patient and through information obtained from the patient, family members, friends or others (Cordell et al., 2013; U.S. Government Publishing

Office, 2016). There are currently no established guidelines regarding the utilization of a formal assessment scale. Conducting cognitive assessments can be time consuming for the providers and can be difficult to incorporate into a time-limited visit. There are numerous validated cognitive screening assessments, however most require an administrator to conduct the assessment via a formal interview, which can be difficult to incorporate into a primary care visit. Primary care providers are in need of an easily administered cognitive screening instrument.

The Self-Administered Gerocognitive Examination (SAGE) (Scharre et al., 2010) is a reliable and valid assessment that is used to detect MCI and early dementia. It is a pen and paper assessment that has 4 interchangeable versions. Since it is self-administered it does not require an administrator to conduct the assessment and it can be conducted in almost any setting (Scharre, Chang, Nagaraja, Yager-Schweller, & Murden, 2014). The digital version of SAGE (eSAGE; commercially known as BrainTest®) is made for tablet use, consists of the identical test questions as SAGE, and is strongly associated with the validated SAGE (Scharre, Chang, Nagaraja, Vrettos & Bornstein, 2017). Both SAGE and eSAGE are tools with high specificity for cognitive impairment (Scharre et al., 2010; Scharre, Chang, Nagaraja, Vrettos & Bornstein, 2017). The SAGE and eSAGE contains questions that are more difficult than other cognitive screening instruments, such as the Mini Mental Status Exam (M. Folstein, S. Folstein, & McHugh, 1975). This allows for the detection of mild impairments. The SAGE or eSAGE could be easily incorporated into the Primary Care Provider Visit since it does not take any additional time from the provider or medical staff to administer. It could potentially allow providers to detect cognitive impairments at the initial visit or it could be used to establish a baseline score to detect changes when given yearly over time. Identification of potentially clinically relevant cognitive changes would then warrant further investigation.

Thus far no large randomized trial has demonstrated a correlation between screening and improved outcomes. This would need to be done to gain widespread acceptance of screening and case finding programs. Early detection of cognitive impairment could potentially result in the appropriate treatment of reversible cognitive impairment conditions or earlier initiation of pharmacological interventions for the management of a variety of other dementia or MCI conditions. A screening approach that reduces the number of false positive screens would improve the comfort level of physicians and patients with cognitive screening programs.

We propose to use SAGE and eSAGE to identify patients who score in the cognitive impairment range during an office visit with their primary care provider. Conversation with an individual who knows the patient well (if possible) will be performed to ascertain a significant change in the patient's cognitive skills over the previous year. We wish to determine if screening for cognitive impairment in this way leads to new diagnoses and management outcomes compared to a group of primary care providers who use their current usual method in screening for cognitive impairment during office visits.

Study Objectives and Aims

Specific Aim 1: To determine if the use of SAGE or eSAGE during a patient's office visit with their primary care provider in combination with any available input from an informant regarding cognitive change over the previous year in that individual will lead to (a) more new diagnoses and/or (b) to new management outcomes by the provider than the usual method (based on the primary care provider's normal practice) currently used for screening for cognitive impairment during such visits.

Specific Aim 2: To determine if cognitive impairment, based on using SAGE or eSAGE, by itself, during a patient's office visit with their primary care provider will lead to (a) more new diagnoses and/or (b) to new management outcomes by the provider than the usual method (based on the primary care provider's normal practice) currently used for screening for cognitive impairment during such visits.

Hypothesis

We hypothesize that the determination of cognitive impairment using the SAGE or eSAGE with and without determination of significant cognitive change over the previous year by an informant, during a patient's office visit with their primary care provider will lead to more new diagnoses and/or new management outcomes than standard of care practices used for screening for cognitive impairment.

Methods and Design

A. Subject Selection

1. Inclusion Criteria
 - a. Adults 65-89 years of age who complete a non-acute care office visit.
2. Exclusion Criteria
 - a. Diagnosis of mild cognitive impairment or dementia in the medical records.
 - b. Diagnosis of visual loss or conditions causing visual loss in the medical records unless it is clear that the loss would not be sufficient to preclude reading standard medical forms with or without the use of visual aids.

B. Method

The Ohio State University Wexner Medical Center has over 100 primary care providers who see patients at 14 offices in central Ohio. These providers routinely see geriatric patients and routinely conduct Annual Wellness Visits.

At least two primary care offices will be involved in this trial. At least one location will serve as the control office and will continue to conduct their visits including screening for cognitive impairment as they normally do using their usual method based on the primary care provider's normal practice. At least one different location will serve as the intervention office where all the providers, as their standard of care, use a standardized method for screening for cognitive impairment consisting of using the SAGE or eSAGE test and having a conversation with an individual who knows the patient well (if possible) to ascertain if a significant change (based on primary care provider opinion) occurred in the patient's cognitive skills over the previous year.

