2. Proportions of subjects in the intervention and the two control groups with any referral for further evaluation/management of potential cognitive impairment (among 10 listed items).
3. Proportions of subjects in the intervention and the two control groups with at least one follow-up visit for additional investigation of a cognitive impairment disorder.

Secondary Outcome Measures

1. Number of referrals (among the 10) used for subjects in the intervention and control groups for further evaluation/management of potential cognitive impairment.
2. Proportions of subjects with pharmacological interventions for the management of the cognitive impairment in the two subgroups of the intervention arm with and without additional inputs from informants.
3. Differences of SAGE and eSAGE scoring between intervention office and research site.
4. Results of the questionnaire to evaluate the practicality and ease of use of the SAGE and eSAGE test by primary care providers and staff.

D. Sample Size Choice and Statistical Analysis Strategy

The power analysis is done using the primary outcome measure of the proportion diagnosed of cognitive impairments. With anticipated proportions of diagnosis of 0.05 (=1/20) and 0.17 (Alzheimer's Association, 2017) for the control and SAGE groups, respectively, and chosen sample sizes of 100 each, a two-sample test of proportions carried out with a two-tailed level of significance of 0.05 will have 78% power to detect the difference. (Our statistical strategy uses more powerful techniques.) We will have data from 100 subjects each from the two control and one intervention group.

For comparing the proportions between the 3 groups (all primary outcome measures and the second secondary outcome measure), we will use a logistic regression model that will control for all relevant covariates including age, gender, race, and income and education levels. The number of referrals (first secondary outcome measure) will be compared using a Poisson regression model that will also control for relevant covariates. Given enough subjects are tested using eSAGE, we will compare the proportions from the SAGE and eSAGE groups. Software JMP Version 14 or later (SAS Institute, Cary NC) will be used for analysis and model diagnostics will be performed to validate the chosen statistical models. Level of significance will be set at 0.05 and adjustments will be made for multiple tests as appropriate.

E. Subjects

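### Visits made for a memory complaint are eligible but not identified, so unequal shares across the non-randomised groups can bias all three primary comparisons in either direction

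*Combined protocol and SAP*

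**What the plan says.** All references are to the combined protocol and SAP.

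- **A. Subject Selection.** The inclusion criterion is "Adults 65-89 years of age who complete a non-acute care office visit". Non-acute is not defined. The exclusions are "Diagnosis of mild cognitive impairment or dementia in the medical records" and visual loss. Neither a presenting memory complaint nor an open cognitive work-up is mentioned.
- **Study Objectives and Aims.** Both aims compare SAGE or eSAGE with the "usual method (based on the primary care provider's normal practice) currently used for screening for cognitive impairment during such visits".
- **B. Method and E. Subjects.** Control group 1 comes from other offices. The intervention office is split by whether the patient completed the test: completers form the Intervention group and non-completers form Control group 2. No randomisation is described, and the first 100 eligible charts fill each group. The review covers demographics, medical history and medications, among other items, within 60 days of the visit. Reason for visit is not listed.
- **C. Outcome Measures.** The three primary outcomes are diagnosis (measured by drug treatment for cognitive impairment), any referral, and at least one follow-up visit for cognitive investigation.
- **D. Sample Size Choice and Statistical Analysis Strategy.** "With anticipated proportions of diagnosis of 0.05 (=1/20) and 0.17" for control and SAGE, with "chosen sample sizes of 100 each", a test "carried out with a two-tailed level of significance of 0.05 will have 78% power to detect the difference". The logistic model controls for relevant covariates; those named are age, gender, race, income and education.

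**The concern.** The trial asks what screening adds. When a patient comes because of memory trouble, a referral, return visit or diagnosis may simply answer the complaint. Such a visit can score on any of the three primary outcomes whether or not SAGE was given.

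This would matter less if the groups were randomised, because the share of such visits would then balance on average. Here offices may differ in how many complaint visits they see. Inside the intervention office, the reason for the visit may also influence whether the test gets done. The plan's examples of reasons for non-completion include lack of time and provider oversight, and both are plausibly less likely when memory is why the patient came. As written, the data would not show whether the shares differ, and the model has no named term for it.

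At stake is whether a difference between groups, or the lack of one, can be attributed to screening.

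**Working it through.** **1. The plan's own figure.** Inputs from section D: p1 = 0.05, p2 = 0.17, n = 100 per group, two-sided 0.05. With the pooled-variance normal approximation:

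power = Φ{[d − 1.96·√(2·p̄(1−p̄)/n)] / √[p1(1−p1)/n + p2(1−p2)/n]}

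Here d = 0.12 and p̄ = 0.11, so power = Φ[(0.12 − 0.0867)/0.0434] = 77.8%. The stated 78% reproduces.

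**2. Assumptions that the documents do not supply.** Let m be the share of complaint visits in a group and q the event rate in those patients. Neither is given. I take m = 5% overall and q = 20%, 50% or 80%. The upper value is more plausible for referral or follow-up than for drug treatment within 60 days.

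**3. Unequal shares, no SAGE effect.** Every other patient has the planned control rate of 0.05. Suppose all complaint patients and half of the others complete SAGE. Then:

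- share among completers = 0.05 / (0.05 + 0.95 × 0.5) = 0.0952
- share among non-completers (Control group 2) = 0
- share in Control group 1 = 0.05

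Extra complaint patients displace patients who have a 5% rate themselves, so the false difference is (difference in shares) × (q − 0.05).

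| q | vs Control group 1: 0.0452 × (q − 0.05) | vs Control group 2: 0.0952 × (q − 0.05) |
|---|---|---|
| 20% | 0.7 points | 1.4 points |
| 50% | 2.0 points | 4.3 points |
| 80% | 3.4 points | 7.1 points |

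At q = 50% the rates are 0.093 (Intervention), 0.0725 (Control group 1) and 0.05 (Control group 2). Exact enumeration of the uncorrected chi-square test puts the chance of a significant result at about 8% and 22%, against a nominal 5%. At q = 20% it is about 5% and 7%.

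**4. The direction is not fixed.** Keep the planned effect in other patients and set q = 50%.

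- Shares of 10% (Intervention) and 5% (control): 0.90 × 0.17 + 0.10 × 0.5 = 0.203 against 0.95 × 0.05 + 0.05 × 0.5 = 0.0725. The difference is 0.1305, which is inflated.
- Shares of 5% and 10%: 0.95 × 0.17 + 0.05 × 0.5 = 0.1865 against 0.90 × 0.05 + 0.10 × 0.5 = 0.095. The difference is 0.0915, which is shrunk, with power 46%.

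**5. Equal shares.** Two further assumptions are needed: that 0.05 and 0.17 describe complaint-free patients, and that SAGE adds nothing in complaint patients. The rates become 0.95 × 0.05 + 0.05q and 0.95 × 0.17 + 0.05q, so the difference is 0.114 for every q.

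| q | Control | SAGE | Power |
|---|---|---|---|
| 20% | 0.0575 | 0.1715 | 71.9% |
| 50% | 0.0725 | 0.1865 | 67.3% |
| 80% | 0.0875 | 0.2015 | 63.2% |

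**The case against.** **Planning rates.** Section D gives 0.05 as the anticipated proportion in a control group whose eligibility already admits complaint visits. Read that way, their events are inside 0.05 and 0.17, and step 5 counts them twice. A 5% share at q = 80% would leave the other control patients a rate of only (0.05 − 0.04)/0.95 = 1.1%. The documents do not say which population the rates describe, so this stands against any flat claim of lost power.

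**No SAGE effect in complaint patients.** The Introduction reports long delays to diagnosis and many undiagnosed cases, so SAGE might change management in symptomatic patients too. This also stands.

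**Share.** The Introduction says "Often, adults who experience subjective memory complaints do not discuss the symptoms with their physician", so such visits may be few. This limits the size of the effect but not the route to bias.

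**Completion pattern.** The split in step 3 is hypothetical. All intervention-office providers are meant to use the test, and impaired patients might complete it less often, which would reverse the sign. This is correct, and it is why no direction can be claimed.

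**Scope.** The aims speak of office visits generally and never restrict them to patients without a complaint. A mixed population may be a deliberate choice. That stands as a reason to keep the all-eligible result, but not as a reason to leave the reason for visit unrecorded.

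**Existing adjustment.** The covariate list is open-ended and medical history is reviewed, so a complaint indicator could be added. Nothing commits the plan to that, or to abstracting the field in the same way in every group.

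**Conclusion.** The gap is real. Complaint-driven visits are eligible in all three groups, can produce every primary outcome without SAGE, and are neither listed for abstraction nor named for adjustment in a comparison without randomisation. Unequal shares can bias all three primary comparisons in either direction.

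The size is unknown. In the illustration the false difference runs from 0.7 to 3.4 points against Control group 1 and from 1.4 to 7.1 points against Control group 2; the difference used for planning is 12 points. It rests on an assumed 5% share, the assumed completion pattern, q between 20% and 80%, a 5% rate in other patients and no SAGE effect.

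A reader might infer that these visits necessarily dilute the planned difference, or that the 78% power is wrong. The documents support neither. The power figure is correct for its inputs. The fall to between 71.9% and 63.2% holds only if the planning rates describe complaint-free patients and SAGE adds nothing in the others. Nor do the documents show that the bias favours SAGE, or that the aims exclude patients with a presenting complaint.

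**What to change.** Define non-acute. In the chart review already planned, abstract one indicator for every subject in all three groups: a cognitive complaint, a cognitive-symptom code or an open cognitive work-up. Take it only from entries dated before the index visit or from the scheduled reason for that visit. This gives the same anchor in groups where no test was completed and keeps the indicator from being influenced by the test result.

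Base the screening conclusion on patients without the indicator. Report the others as a separate stratum, with the share in each group. Give the all-eligible result, adjusted for the indicator, as a sensitivity analysis.

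The cost is one added field and a few more charts to fill each group. The main conclusion then applies only to patients with no presenting cognitive complaint, which is narrower than the aims as worded and should be stated. The change does not cure the wider problem of groups defined by test completion.

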2. Proportions of subjects in the intervention and the two control groups with any referral for further evaluation/management of potential cognitive impairment (among 10 listed items).
3. Proportions of subjects in the intervention and the two control groups with at least one follow-up visit for additional investigation of a cognitive impairment disorder.

Secondary Outcome Measures

1. Number of referrals (among the 10) used for subjects in the intervention and control groups for further evaluation/management of potential cognitive impairment.
2. Proportions of subjects with pharmacological interventions for the management of the cognitive impairment in the two subgroups of the intervention arm with and without additional inputs from informants.
3. Differences of SAGE and eSAGE scoring between intervention office and research site.
4. Results of the questionnaire to evaluate the practicality and ease of use of the SAGE and eSAGE test by primary care providers and staff.

D. Sample Size Choice and Statistical Analysis Strategy

The power analysis is done using the primary outcome measure of the proportion diagnosed of cognitive impairments. With anticipated proportions of diagnosis of 0.05 (=1/20) and 0.17 (Alzheimer's Association, 2017) for the control and SAGE groups, respectively, and chosen sample sizes of 100 each, a two-sample test of proportions carried out with a two-tailed level of significance of 0.05 will have 78% power to detect the difference. (Our statistical strategy uses more powerful techniques.) We will have data from 100 subjects each from the two control and one intervention group.

For comparing the proportions between the 3 groups (all primary outcome measures and the second secondary outcome measure), we will use a logistic regression model that will control for all relevant covariates including age, gender, race, and income and education levels. The number of referrals (first secondary outcome measure) will be compared using a Poisson regression model that will also control for relevant covariates. Given enough subjects are tested using eSAGE, we will compare the proportions from the SAGE and eSAGE groups. Software JMP Version 14 or later (SAS Institute, Cary NC) will be used for analysis and model diagnostics will be performed to validate the chosen statistical models. Level of significance will be set at 0.05 and adjustments will be made for multiple tests as appropriate.

E. Subjects

Three hundred subjects will be enrolled in the trial equally divided between the three arms: Control group 1, SAGE/eSAGE completers in the intervention office (Intervention group) and SAGE/eSAGE non-completers in the intervention office (Control group 2). The 100 subjects for each group will consist of the first 100 eligible subjects based on the record review.

F. Informed Consent

A waiver of written informed consent will be requested of the IRB for this trial. We will be comparing standard of care practices at two primary care offices. One location will incorporate the SAGE or eSAGE test and informant question into their standard of care practice for screening for cognitive impairment. The other location will conduct screening for cognitive impairment as they normally do. Since we are comparing standard of care practices there is no more than minimal risk to the subjects. Results are only recorded in the aggregate.

G. Data Collection and Management

This study will utilize REDCap (Research Electronic Data Capture), a software toolset and workflow methodology for electronic collection and management of clinical and research data, to collect and store data. The Ohio State Center for Clinical and Translational Science (CCTS) Research Informatics Services will be used as a central location for data processing and management. REDCap provides a secure, web-based application that provides an intuitive data manipulation interface, custom reporting capabilities, audit trail functionality, real-time data monitoring/querying of participant records, and variations of data exporting/importing. REDCap is hosted by OSUWMC IT in the Ackerman Datacenter ([name]).

REDCap instance is located outside of the OSUWMC network. Non-PHI Redcap is accessible from any internet connection. No encrypted VPN tunnel is required.

REDCap supports electronic signatures by positively identifying the user through a unique username and password combination. The provisioning of accounts and user access to specific database(s) is integrated with the OSUWMC LDAP authentication service for studies

containing protected health information (PHI), the provisioning of access and specific user rights for all studies and review of content are managed by CCTS staff.

Risk-Benefit Analysis

The risks to the subjects are very low. Possible risks include anxiety associated with the completion of the SAGE or eSAGE test and having an informant give their opinion of the patient's cognition change over time. The seriousness of this risk is very low. Possible benefits to the subjects include the potential of early detection of cognitive impairments.

IRB/Patient Confidentiality

The Biomedical Sciences Institutional Review Board (IRB) at The Ohio State University will be the IRB for this trial. All of the study materials, including the study measures, will be reviewed by the IRB prior to the start of the trial. If any ethical concerns are identified they will be addressed, and the protocol will be amended, to ensure proper ethical conduct of the trial and the protection and safety of the participants. Once IRB approval is obtained the trial will begin. IRB oversight will occur throughout the entire trial.

To protect the privacy and confidentiality of the participants, all of the paper records for the trial will be kept in secured locked rooms/cabinets so that privacy of the subject's data is maintained. The only people who will have access to the records are the study investigators and their staff. Digital data stored for this study will be kept on a server inside the firewalls at the outpatient clinics and will be password protected. All data used for analysis is in aggregate and will be deidentified prior to analyses.

REFERENCES

1. Adams, M. (2016). Routine Check-Ups and Other Factors Affecting Discussions With a Health Care Provider About Subjective Memory Complaints, Behavioral Risk Factor Surveillance System, 21 States, 2011. *Preventing Chronic Disease*, 13, E15. <http://doi.org/10.5888/pcd13.150471>
2. Alzheimer's Association. (2015). Alzheimer's Facts and Figures. Retrieved from http://www.alz.org/alzheimers_disease_facts_and_figures.asp#quickFacts
3. Alzheimer's Association. (2017). Alzheimer's Association Report 2017 Alzheimer's disease facts and figures. *Alzheimer's & Dementia*, 13, 325-373.
4. Alzheimer's Disease International (ADI). (2016). Dementia Statistics. Retrieved from <https://www.alz.co.uk/research/statistics>
5. Barnes, D. E., Beiser, A. S., Lee, A., Langa, K. M., Koyama, A., Preis, S. R., ... Weir, D. R. (2014). Development and validation of a brief dementia screening indicator for primary care. *Alzheimer's & Dementia*, 10(6), 656-665.e1. <http://doi.org/10.1016/j.jalz.2013.11.006>

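### Section D compares three groups without naming a contrast, so a primary result could turn on Control group 2 and not on SAGE against usual care

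*Combined protocol and SAP*

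**What the plan says.** The Hypothesis section is directional and has one comparator: SAGE or eSAGE, with or without informant input, will lead to "more new diagnoses and/or new management outcomes than standard of care practices used for screening for cognitive impairment". Both Specific Aims use the same comparator, the provider's usual method.

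Section B defines two control groups. Control group 1 comes from offices that did not use SAGE or eSAGE at all. Control group 2 is made up of intervention-office patients who did not complete the test; lack of time, patient noncompliance and provider oversight are given as possible reasons. The same section says that providers at the intervention office use SAGE or eSAGE plus an informant conversation as their standard practice. Section C states each primary outcome for the intervention group and both control groups together.

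Section D sizes the study as a two-group problem. It starts "With anticipated proportions of diagnosis of 0.05 (=1/20) and 0.17" and concludes that "a two-sample test of proportions carried out with a two-tailed level of significance of 0.05 will have 78% power to detect the difference". It then adds: "We will have data from 100 subjects each from the two control and one intervention group". The analysis sentence begins "For comparing the proportions between the 3 groups (all primary outcome measures and the second secondary outcome measure" and goes on to name a logistic regression model with covariate control. Adjustment for multiple tests is promised as appropriate, with no method and no count of tests. No contrast, primary comparator or role for Control group 2 is stated.

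**The concern.** The question is two-group, the sample size is two-group, and the described analysis is three-group. Nothing connects them.

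This would matter little if the two control groups were interchangeable, but they are not. They come from different offices and providers. Control group 2 is selected by whatever led to non-completion, and its providers had adopted the new screening method. Its rate could lie below usual care (for example, if visits were hurried) or above it (for example, if impaired patients tend not to finish the test). Either way, a difference between the controls could produce a significant result while SAGE does nothing against usual care. With the decision rule open, the comparison that carries the conclusion can be chosen after the results are seen. The stated power belongs to a contrast that the analysis section never names.

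**Working it through.** **Inputs from the documents (Sections D and E).** Control rate 0.05, SAGE rate 0.17, 100 per group in three groups, two-sided 0.05, stated power 78%. **Assumed:** every Control group 2 rate. Covariates and clustering by office or provider are ignored.

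**1. The plan's own figure.** Pooled normal approximation, mean rate 0.11:
- SE under the null = √(2 × 0.11 × 0.89 / 100) = 0.04425
- SE under the alternative = √(0.05 × 0.95 / 100 + 0.17 × 0.83 / 100) = 0.04343
- Power = Φ[(0.12 − 1.960 × 0.04425) / 0.04343] = Φ(0.766) = 77.8%

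This reproduces the stated 78% for one unadjusted two-group contrast.

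**2. No SAGE effect against usual care.** With ℓ(x, n) = x log(x/n) + (n − x) log(1 − x/n), the global statistic is 2[Σℓ(x_g, 100) − ℓ(Σx_g, 300)], compared with 5.991 (2 df). Each pairwise statistic has the same form on two groups, compared with 3.841 (1 df). There were 400,000 simulated trials per row, with SAGE = Control group 1 = 0.05.

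| Control group 2 (assumed) | Global 2-df significant | SAGE vs Control 2 significant | Direction of the latter | SAGE vs Control 1 significant |
|---|---|---|---|---|
| 0.01 | 44% | 49% | favours SAGE | 6.5% |
| 0.02 | 23% | 26% | favours SAGE | 6.5% |
| 0.05 | 6.3% | 6.5% | either | 6.5% |
| 0.10 | 30% | 28% | against SAGE | 6.5% |
| 0.12 | 48% | 45% | against SAGE | 6.5% |
| 0.17 | 85% | 81% | against SAGE | 6.5% |

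The likelihood-ratio test is slightly liberal at these low rates, which explains the 6.3% to 6.5% where the null holds. With a pooled z test, SAGE vs Control group 1 rejects in about 4%.

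**3. Planned SAGE effect.** SAGE = 0.17, Control group 1 = 0.05. The direct contrast has 81% power by likelihood ratio; the plan's 78% is the normal approximation to the same comparison.

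| Control group 2 (assumed) | Global 2-df power | Direct contrast |
|---|---|---|
| 0.02 | 97% | 81% |
| 0.05 | 85% | 81% |
| 0.11 | 72% | 81% |
| 0.14 | 76% | 81% |
| 0.17 | 84% | 81% |

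The global test has less power only at intermediate rates. It has equal or more power when Control group 2 is near or below 0.05 or near 0.17.

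**The case against.** A reader might infer that the plan commits to a single all-at-once test whose null is equality of all three proportions. The documents do not say so. Section D names a model, and a logistic model with a three-level group term yields the SAGE contrast with each control directly. The two-sample power calculation and the promised multiple-test adjustment fit pairwise testing at least as well. That objection stands, so the global-test figures are conditional on one reading.

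A reader might also take 30% to 85% as the rate of false claims for SAGE. That does not follow. At assumed Control group 2 rates of 0.10 to 0.17, the group that stands out is Control group 2, and the hypothesis is directional. If an analyst also required SAGE to be significantly above Control group 1, false support would fall to about 2% to 3%. This stands too, but the plan does not state that requirement.

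Nor is power generally lost. At the plan's single control rate of 0.05 for both controls, the global test has more power (85% against 81%).

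Reading the plan as pairwise does not close the gap. Two SAGE contrasts would then exist with no ranking, and the one against Control group 2 can favour SAGE in 26% to 49% of trials when SAGE equals usual care. Multiplicity adjustment limits how often tests err under their own nulls. It does not say which null bears on the hypothesis.

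**Conclusion.** The concern holds as an unspecified primary contrast, not as a wrong test prescribed by the plan. Under either reading of Section D, a significant primary result could arise from Control group 2 alone: about 30% to 85% for a global test with Control group 2 at 0.10 to 0.17, and about 26% to 49% in SAGE's favour for an unranked pairwise test with Control group 2 at 0.02 to 0.01. The contrast that answers the hypothesis rejects in about 4% to 6.5%. These sizes rest on assumed Control group 2 rates, equal underlying rates of 0.05 for SAGE and Control group 1, and independent patients without covariates. If Control group 2 really sits at 0.05, the inflation disappears. The plan should be changed, because the remedy is small and the two controls differ by design.

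**What to change.** In Section D, keep the logistic model and add that, for each primary outcome, the 1-df contrast Intervention vs Control group 1 is the test of the hypothesis. Report Intervention vs Control group 2 and Control group 1 vs Control group 2 as supporting estimates with confidence intervals. State that neither an overall group test nor the Control group 2 contrast alone counts as evidence for SAGE over usual care.

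This costs a sentence or two and needs no new data or subjects. The 78% then belongs to the named contrast, before any multiplicity adjustment. For scale, the formula in the working gives 62.7% with Bonferroni over the three primary outcomes (0.05/3). Keeping both SAGE contrasts confirmatory on one outcome (0.025 each) would give 68.4% per contrast. The price is that Control group 2 loses confirmatory status. The change also does not remove confounding between offices or selection of completers, since allocation is not randomised.
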